### **3 DATASETS ANALYZED**

Subjects who were not eligible for randomization but who have been erroneously randomized into the study will be excluded from all datasets analyzed, if they did not receive study product.

The populations of analysis will be reviewed and confirmed by the sponsor prior to database lock.

#### **3.1 Intent-To-Treat (ITT) Population**

The Intent-To-Treat Population will include all participants who were randomized [a randomization number is provided in the eCRF Form “Randomization”] and received at least 1 dose of study drug [as confirmed in the eCRF Form “Study Drug Administration”] and not reported as a screen failure [in the eCRF Form “Disposition-Study Completion” ]. Participant data will be summarized by treatment assigned.

#### **3.2 Per-Protocol Population**

The Per Protocol (PP) Population will include all participants from the ITT population who have no important study protocol deviations during the study. Because the number of days on study medication is likely to impact the efficacy endpoints, patients who will deviate from the protocol by not taking study medication at least 5 days (as assessed by the difference between date of study treatment last dose – date of study treatment first dose + 1 day) will be excluded. These patients shall be excluded from the PP population prior to database lock.

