**Table 2: Treatment Details**

Study Treatment Name:	Dalcetrapib (or matching placebo tablets)
Dosage Formulation:	Film-coated white to off-white tablets
Unit Dose Strength(s)	300 mg per tablet
Route of Administration:	Oral (recommended to be taken with the largest meal of the day)
Dosing Instructions:	

For 900 mg dose: 3 active tablets and 9 placebo tablets

For 1800 mg dose: 6 active tablets and 6 placebo tablets

For 3600 mg dose: 12 active tablets

Placebo dose: 12 placebo tablets

Packaging and Labeling:	The tablets can be stored in glass and plastic bottles or aluminum blisters. The recommended storage conditions are on the packaging and should be followed. For batch specific details and information on shelf-life, see the packaging.
Manufacturer:	Dalcetrapib tablets: Recipharm, Leganés, Spain Placebo tablets: Catalent, Kansas City, MO, United States

The physicochemical properties and the pharmaceutical specifications of dalcetrapib are provided in the Investigator's Brochure.

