### 5.2. Preparation, Storage, Handling, and Accountability

The study drug will be supplied by the Sponsor (or designee), along with the batch/lot numbers and Certificates of Analysis. A Certificate of Release authorized by a Qualified Person in the European Union will also be issued for the investigational medicinal product. The study treatment will be provided in bottles, 10 bottles with 12 tablets per bottle, with 1 bottle to be taken per day.

The Investigator or designee must confirm appropriate temperature conditions have been maintained during transit for all study treatment received and any discrepancies are reported and resolved before use of the study treatment.

All study treatments must be stored in a secure, environmentally controlled, and monitored (manual or automated) area in accordance with the labeled storage conditions with access limited to the Investigator and authorized site staff.

Only patients enrolled in the study may receive study treatment and only authorized site staff may supply study treatment. The Investigator, institution, or the head of the medical institution

(where applicable) is responsible for study treatment accountability, reconciliation, and record maintenance (i.e., receipt, reconciliation, and final disposition records).

Further guidance and information for the final disposition of unused study treatment are provided in a separate document.

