### **5.5. Treatment Compliance**

Records shall be maintained of the delivery of study treatment to the study sites, the inventory at the study sites, the use for each patient, and the return to the Sponsor.

These records shall include dates, quantities, batch/lot information, expiry dates, and the unique code numbers assigned to the study treatment and study patients.

---

The Investigator shall be responsible for ensuring that the records adequately document that the patients were provided the doses specified in the protocol and that all study treatment received from the Sponsor is reconciled.

Site staff will monitor compliance of patients with their assigned randomized treatment (dalcetrapib 900, 1800, or 3600 mg or placebo) by recording the number of tablets actually used.

For patients who are hospitalized, patients will be administered treatment by the site staff during hospitalization. On discharge, all patients are to be reminded of the importance of compliance with the treatment with an emphasis on taking their study treatment on schedule and contacting the study site for an appointment as soon as possible if they think they are experiencing worsening of condition.

Compliance information will be captured via eSource (if a patient version is used) or telemedicine. Patient will return unused supply at the EOT visit.

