### 6.3.5 Treatment Compliance

Compliance will be assessed if subject took all the pills at each study visit and will be summarized using frequencies and percentages, by treatment group, for the subjects of the ITT population. If subject did not take all the pills, then the number of missed pills will be reported as number of patients (n), mean, standard deviation, median, Q1, Q3, minimum, and maximum.

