#### 6.5.1 Treatment Exposure

Duration of exposure will be defined as number of days on treatment for each subject. Duration will be calculated as: [treatment end date – treatment start date + 1] from the eCRF Form “Study Drug Administration”.

Duration of exposure will be summarized by treatment arm using N, mean, median, standard deviation, Q1, Q3, minimum and maximum.

Duration of exposure will also be categorized according to day intervals ([1-3], [4-5], [6-7], [8-9], [10], [>10]) and summarized using frequencies and percentages, overall and by treatment group.

In addition, if subject interrupted/discontinued the study medication, then the reason will also be reported using frequencies and percentages overall and by treatment group.

Duration of exposure will be presented for the safety population.

A listing with details on the administration of study medication will be provided (Section 7, Listing 6).

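### The per-protocol dosing rule and the exposure table measure days on medication as a calendar span from first to last dose, which over-counts whenever doses are skipped

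*SAP*

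**What the plan says.** SAP 3.2 defines the per-protocol (PP) set as "all participants from the ITT population who have no important study protocol deviations during the study". It then adds one explicit dosing criterion. Because time on drug is expected to influence the efficacy endpoints, it excludes "patients who will deviate from the protocol by not taking study medication at least 5 days", and the days are to be counted "as assessed by the difference between date of study treatment last dose – date of study treatment first dose + 1 day".

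SAP 6.5.1 describes duration of exposure as days on treatment and computes it as "treatment end date – treatment start date + 1". The result is grouped into 1-3, 4-5, 6-7, 8-9, 10 and >10 days. Reasons for interruption or discontinuation are tabulated alongside, but gap days are not subtracted.

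Other parts of the plan bear on what was actually taken:

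- Protocol 5.2: supply is "10 bottles with 12 tablets per bottle, with 1 bottle to be taken per day". Appendix 4 has the drug self-administered once daily on Days 1 to 10.
- Protocol 5.5: site staff monitor compliance "by recording the number of tablets actually used", and unused supply is returned.
- SAP 6.3.5: "Compliance will be assessed if subject took all the pills at each study visit". Missed pills are then summarised by arm in a compliance table of their own.

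Neither SAP 3.2 nor SAP 6.5.1 draws on the tablet counts.

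**The concern.** In both sections the quantity named (days of taking medication, days on treatment) differs from the quantity computed (elapsed days between two dates) as soon as a dose is skipped between them. Such gaps are foreseen: SAP 6.5.1 tabulates reasons for interruption, and Protocol Appendix 1 lists temporary interruption among the actions taken for an adverse event.

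Two outputs are at stake. The PP analysis repeats the primary analysis in patients with adequate treatment, and its only written dosing criterion can be met by someone who took very little. The exposure table supports the reading of the safety data, and it can place a patient with large gaps beside a patient who completed the course.

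**Working it through.** **Inputs.** Threshold of 5 days and the span formula (SAP 3.2); the same formula and the exposure categories (SAP 6.5.1); once-daily dosing on Days 1 to 10 (Protocol Appendix 4); 12 tablets a day for 10 days, so 12 × 10 = 120 tablets (Protocol 5.2).

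**Formula.** Span = last dose day − first dose day + 1.

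**Uninterrupted dosing reproduces the intended count.** Days 1 to 5: 5 − 1 + 1 = 5, with 5 doses. Days 1 to 10: 10 − 1 + 1 = 10, with 10 doses. Stopping after Day 4 gives 4 and fails, as intended.

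**Interrupted dosing does not.**

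| Doses taken on | Span | Doses | Tablets of 120 | 5-day rule by span | 5-day rule by doses | Exposure category by span | by doses |
|---|---|---|---|---|---|---|---|
| Days 1 and 5 | 5 | 2 | 24 (20%) | met | not met | 4-5 | 1-3 |
| Days 1 and 10 | 10 | 2 | 24 (20%) | met | not met | 10 | 1-3 |

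**Direction of the error.** With at most one dose a day, doses taken can never exceed the span, so the formula can only over-count. Listing every pattern that starts on Day 1 and ends by Day 10 gives 2^9 = 512. Those with span of at least 5 but fewer than 5 doses have a last dose on day s (s = 5 to 10) and 0, 1 or 2 doses on the s − 2 days in between:

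- 2 doses: 6 patterns
- 3 doses: 3 + 4 + 5 + 6 + 7 + 8 = 33
- 4 doses: 3 + 6 + 10 + 15 + 21 + 28 = 83

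The total is 6 + 33 + 83 = 122. No pattern has 5 or more doses with a span below 5. The 122 counts possible patterns; it is not an expected frequency.

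**The >10 category.** With ten one-day bottles and one bottle a day, a span above 10 requires at least one undosed day. A patient who skips two days and then finishes the supply shows 10 + 2 = 12. The longest exposure category would therefore hold patients with gaps, not patients with more drug.

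**The case against.** The case on the other side has four parts.

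- **Important deviations.** The PP set also requires no important protocol deviations, and SAP section 3 has the sponsor confirm the populations before database lock. Two doses out of ten departs from the schedule and could be excluded on that ground. This stands as far as it goes: retention is not certain. Exclusion is not certain either, because the SAP does not define an important deviation and sets no missed-dose threshold. A patient who passes the only written dosing criterion can be removed only by unstated judgement.
- **Early stopping is handled correctly.** Protocol 5.3.1 does not allow dose modification; a patient who needs one is discontinued. For a patient who simply stops, the span is exact. This stands, and the error is confined to courses with gaps.
- **Missed pills are reported.** The compliance table (Table 1.4.1) shows them by arm, and a listing covers drug administration, so the information is not lost. But it feeds neither formula, and the compliance and exposure tables can give conflicting pictures of the same patient.
- **The stakes are limited.** The PP set serves only a sensitivity analysis of the primary endpoint. This stands.

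**Conclusion.** The point holds as a mismatch between label and formula that can misclassify patients in one direction. In the constructed examples, 2 doses count as 5 or 10 days. How often this happens depends on how often doses are skipped, which the documents do not give. The effect is limited to the PP sensitivity analysis and the exposure table; the ITT analysis does not use either formula. The examples assume at most one dose a day and full 12-tablet doses.

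Three stronger readings are tempting and are not supported:

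- **That the PP set will contain barely treated patients.** The important-deviation clause may remove them. What can be said is that the written criterion does not.
- **That exposure is overstated most at 3600 mg.** Every arm, placebo included, takes 12 tablets a day, so pill burden does not single out that arm. Protocol 1.3 mentions gastrointestinal effects but gives no rate of skipped doses by dose.
- **That partial doses make exposure unknowable in the lower arms.** Table 2 does mix active and placebo tablets ("For 900 mg dose: 3 active tablets and 9 placebo tablets"; 6 and 6 at 1800 mg). If tablets were taken in random order, taking 9 of 12 would include all active tablets with probability 84/220 = 0.38 at 900 mg and 20/220 = 0.09 at 1800 mg, while at 3600 mg it would be exactly 9 × 300 = 2700 mg. Random order is an assumption. This is only a caveat for reading missed-pill counts across arms.

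**What to change.** **SAP 3.2.** Keep the 5-day threshold and apply it to medication actually taken. Use the number of days with a recorded dose where that is available; otherwise use the recorded tablet counts, with 5 days' supply equal to 5 × 12 = 60 of 120 tablets. State this order of precedence before the populations are confirmed, because the two measures can differ for a patient who took partial doses.

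Do not require full 12-tablet days. A patient who took 11 of 12 tablets on all ten days would have 110 of 120 tablets (92%) but no full day, and would be dropped. Such a rule would also need daily counts. SAP 6.3.5 assesses compliance by visit, and Protocol 5.5 does not say that tablets are recorded by day.

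**SAP 6.5.1.** Report tablets taken (of 120), or days dosed, by arm as exposure. Keep the present calculation as a separate line labelled time from first to last dose.

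**Cost.** SAP wording and some reprogramming; Protocol 5.5 already provides for recording tablets used. Some patients may leave the PP set, and those with missing counts need a listing.

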#### **3.3 Safety Population**

The Safety Population will include all participants who received at least 1 dose of study drug. Participant data will be summarized by actual treatment received.

### **4 EFFICACY ENDPOINTS**

#### **4.1 Primary Efficacy Endpoint**

The primary efficacy endpoint is:

- Time to sustained clinical resolution of symptoms (excluding cough, sense of smell and taste)

Sustained clinical resolution is defined as occurring when no key COVID-19 related symptom (excluding cough, sense of smell and taste) has a score higher than 1 over a 72-hour period (as documented using an electronic patient-reported outcome [ePRO] instrument or in the eCRF). The time to resolution will be taken as the time from randomization until the first day of the last 72-hour period where the patient meets the definition of resolution within 28 days. Patients who do not meet the definition of resolution 28 days after randomization will be considered not resolved.

The classification of sustained clinical resolution of symptoms (excluding cough, sense of smell and taste) follows similar steps as the algorithm presented in Appendix 1.

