## 2.2. Endpoints

The primary efficacy endpoint is:

- Time to sustained clinical resolution.

Sustained clinical resolution is defined as occurring when no key COVID-19 related symptom has a score higher than 1 over a 72-hour period (as documented using an electronic patient-reported outcome [ePRO] instrument), except for sense of smell and taste (items 13 and 14) where the score should be 0 over a 72-hour period. The time to resolution will be taken as the time from randomization until the first day of the last 72-hour period where the patient meets the definition of resolution within 28 days. Patients who do not meet the definition of resolution 28 days after randomization will be considered not resolved.

The secondary efficacy endpoints are:

- Time to complete clinical resolution
- Change from baseline in COVID-19 total symptom score
- Score on the WHO Clinical Outcome Scale (9-point scale)
- Rate of hospitalization
- Rate of progression to oxygen therapy
- Duration of hospitalization
- Time to viral clearance based on PCR test for SARS-CoV-2
- Change from baseline in log10 viral load
- Mortality rate

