### 3. INVESTIGATION PLAN

#### 3.1. Overall Study Design and Plan Description

This is a randomized, double-blind, multicenter, Phase 2a proof-of-concept study in outpatients with confirmed, mild to moderate, symptomatic COVID-19. Dalcetrapib inactivates the 3CLMpro enzyme of Corona virus and therefore stops the viral replication and transcription in cells. It is being planned to use for treatment in patients with COVID-19.

Up to 60 sites in the United States and Canada, and other countries as appropriate based on the pandemic situation, are planned to enroll patients.

Total duration of study participation is up to 32 days. The screening period is planned to occur between 48 to 24 hours prior to dosing. Randomization will occur during the Screening/Baseline visit in order for treatment to be dispensed in time for start of first dose on Day 1. Patients will either receive dalcetrapib 900, 1800, or 3600 mg or placebo for 10 days and be followed for 18 days of follow-up. The study design is summarized in [Figure 2](#).

It is anticipated that 208 patients will be randomized in one of the dalcetrapib treatment arms or placebo (52 patients to each of 900 mg, 1800 mg, 3600 mg and placebo) for 10 days. Patients will be randomized and receive first dose of study drug within 72 hours of receiving a positive PCR or Point-of-care test for SARS-CoV-2. Patients need to have at least two of the 14 common COVID-19-related symptoms described in the inclusion criteria rated as mild or moderate, as evaluated by ePRO assessment. Symptoms will be assessed at each study visit daily for the first 10 days, then at Day 14 and Day 28, and as clinically indicated. Symptoms will be evaluated as absent, mild, moderate, or severe depending on their impact on activity of daily living.

[figure not shown]
SARS-CoV-2 viral loads will be obtained by both saliva (Oragene) collection and mid-turbinate nasal swab self-collected under supervision of healthcare professional (virtual or home visit) at Screening/Baseline, Day 1, Day 3, Day 5, Day 7, Day 10, and Day 28. Patients who require hospitalization after initiation of study treatment will be followed for vital status through Day 28.

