- a. Screening/Baseline assessments may all be performed on the same calendar day and should be performed at the study site or as a home visit within 72 hours of first dose. Baseline assessments that are also performed at Screening do not need to be repeated if on the same calendar day. Study drug should be dispensed at the Screening/Baseline visit and only taken after the Day 1 virtual visit confirming the positive COVID-19 test has occurred. If the PCR test is negative or laboratory results exclude the patient, they will not take the first dose of study drug and be withdrawn from the study.
- b. Patients will be randomized to receive either 900, 1800, or 3600 mg of dalcetrapib treatment or placebo.
- c. The entry testing is performed locally based on testing methods available at the site, such as PCR or rapid antigen test.
- d. Patients must have at least two mild to moderate signs or symptoms of COVID-19, as described in the inclusion criteria, with onset within 5 days of first dose on Day 1. Symptoms will be assessed daily for the first 10 days, then at Day 14 and Day 28 and as clinically indicated.
- e. Dates of change in WHO scale status between visits will be recorded over the course of the 28-day study period.
- f. SARS-CoV-2 viral loads will be obtained by both saliva (Oragene) and mid-turbinate nasal swab self-collected under supervision of a healthcare professional at Screening/Baseline, Day 1, Day 3, Day 5, Day 7, Day 10, and Day 28.
- g. Two PK samples will be collected on Day 10, one at predose and one at postdose in a sampling window of 0-2, 2-4, 4-6, 6-10, or 10-24 hours postdose. Patients will be evenly randomized to one of the sampling windows on Day 10.
- h. Study drug is self-administered as once daily oral tablets on Days 1 to 10.
- i. In case of screen failure only.

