##### **6.4.2 Key Secondary Analysis**

#### 6.4.2.1 Change from Baseline in log10 Viral Load

Log10 viral load, as assessed using the saliva and as assessed using the nasal swab, will be summarized by treatment group using descriptive statistics (N, mean, median, standard deviation, minimum, and maximum) for each visit as well as for changes from baseline where an 80% CI will also be presented.

Mean changes from baseline will be analyzed using a repeated measures ANCOVA model including effects of treatment, visit (Day 3, Day 5, Day 10 and Day 28/EOS), and treatment-by-visit interaction, as well as baseline value of log10 viral load and baseline value of log10 viral load-by-visit-interaction. An unstructured covariance structure will be used to model the within-patient errors and the Kenward-Roger approximation will be used to estimate denominator degrees of freedom. The combined two highest treatment groups will be compared to placebo in addition to the comparison of individual doses at the following study visits (Day 3, Day 5, Day 10 and Day 28/EOS).

Since oragene and nasal samples are collected by the subjects themselves (visit identifiers may be unreliable), an algorithm (presented in Appendix 2) was developed to classify the day of assessment into their respective visit identifiers. This algorithm is based on the fact that Day 1 corresponds to the date of the first dose and as such, will be used as baseline when available. This is in alignment with the study protocol that identifies Day 1 as the date of first dose. It is understood that all protocol assessments collected on Day 1 were to be done PRIOR to the first dose. Therefore, Day 1 will correspond to baseline when available. Please refer to Appendix 2 for more details.

A plot of mean change from baseline in log10 viral load with 80% CI at each study visit will also be presented (Section 7, Figure 4).

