## 9 APPENDICES

### APPENDIX 1

Algorithm used to classify sustained clinical resolution:

For each subject, all ePRO records will be sorted by the date/time. For each assessment, we characterize the record as clinically resolved (i.e., score of 0 for taste and smell and all other symptoms, a score of 0 or 1) or not.

From Day1 to Day10 (or last ePRO assessment before Day14)

- a) If resolved at Day 10 (or last ePRO assessment), identify first date when resolution occurred with no relapse. This is the tentative date of resolution to be confirmed at Day 14 and Day 28.
- b) If not resolved at Day 10 (or last ePRO assessment), re-assess at Day 14.

At Day14:

- c) If resolved for the first time at Day 14 (i.e. was not resolved at Day 10 or before), use date of Day 14 as the tentative date of resolution to be confirmed at Day 28.
- d) If still resolved at Day 14 (i.e. was already resolved at Day10 or before), use date of resolution identified in step a). This is the tentative date of resolution to be confirmed at Day 28.
- e) If not resolved at Day 14, re-assess at Day28.

At Day28:

- f) If resolved for the first time at Day 28 (i.e., was not resolved at Day 14), subject will be classified as resolved within 28 days and date of resolution will be the date of Day 28.
- g) If still resolved at Day 28 (i.e. was already resolved at Day 14), subject will be classified as resolved within 28 days and date of resolution will be the date of resolution identified in step c) or d).
- h) If not resolved at Day 28, subject will be classified as not resolved within 28 days and the date of censoring will be the date of Day 28.

It should also be noted that subjects who do not have an assessment at Day 28 will be classified as non-resolved REGARDLESS if symptoms were resolved up to their last assessment. Date of censoring will be the date of study discontinuation.

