**APPENDIX 2**

To classify the symptom score and viral load assessments to their appropriate visit identifier, the difference in days between the date of the assessment and the date of the first dose will be calculated, and this difference will be classified according to the reporting windows below. This algorithm will ensure that Day X for symptom score will correspond to Day X for viral load. As per the study protocol, Day 1 corresponds to the date of 1st dose in which all assessments were to be done PRIOR to first dose.

Once the visit identifiers are sorted out, Day 1 will be used to establish a baseline visit. If a subject has no Day 1 assessment but a screening one, then the screening assessment is chosen.

In cases where more than one assessment falls within the same reporting window, the first assessment will be chosen.

Note: For the symptom score, if both ePRO and eCRF assessments were done on the same day, then the ePRO was favored.

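### The SAP's primary log-rank test names no strata, although patients can meet the resolution threshold before dosing; the cost is power, not false positives

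*SAP*

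**What the plan says.** **Entry.** Protocol 3.1 asks for "at least two of the 14 common COVID-19-related symptoms described in the inclusion criteria rated as mild or moderate". Protocol Table 3 scores mild as 1.

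**Endpoint.** In SAP 4.1, resolution means that "no key COVID-19 related symptom (excluding cough, sense of smell and taste) has a score higher than 1 over a 72-hour period". That leaves 14 − 3 = 11 counted items. Protocol 2.2 uses the same cut-off, "no key COVID-19 related symptom has a score higher than 1 over a 72-hour period", but requires 0 for smell and taste and keeps cough.

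**Dating.** SAP 4.1 takes "the first day of the last 72-hour period where the patient meets the definition of resolution within 28 days" and refers to Appendix 1 for the steps. Appendix 1 works through the records from Day 1 and asks to "identify first date when resolution occurred with no relapse", to be confirmed at Day 14 and Day 28. SAP 6.4.2.1 says that "all protocol assessments collected on Day 1 were to be done PRIOR to the first dose", and Appendix 2 says that "Day 1 will be used to establish a baseline visit".

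**Strata.** Protocol 5.3 stratifies randomisation by presence or absence of moderate or severe symptoms and by age (up to 65, over 65). Protocol 8.4.1.1 stratifies the log-rank test by the same two factors. SAP 6.4.1 specifies two-sided log-rank tests and mentions no strata. SAP 1 says the SAP prevails where the two documents differ.

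**Sensitivity analyses.** SAP 6.4.4 repeats the primary analysis in the per-protocol population and with the last observation carried forward to Day 28. SAP 6.4.5 allows a subgroup analysis by variant. None of these separates patients by baseline status on the counted items.

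**The concern.** A patient whose counted symptoms are all mild or absent meets the resolution threshold before treatment starts. One of the two randomisation factors is the absence of moderate or severe symptoms, so the design provides for such patients. The protocol endpoint already had this gap. Dropping cough, smell and taste widens it: a patient whose only score of 2 is for cough now also qualifies at baseline.

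Under Appendix 1, such a patient who never relapses and is confirmed at Day 14 and Day 28 is dated to the pre-dose Day 1 record. For that patient the endpoint records absence of worsening, not recovery. If most of these patients stay at 0–1, they contribute early events that look alike in every arm and weaken the contrast. A test stratified by baseline severity would compare them mainly with each other, and the SAP's wording removes that protection. What is at stake is power for the declared primary comparison, the two highest doses against placebo.

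**Working it through.** **1. The plan's own figure.** Inputs from Protocol 8.1: 127 events, HR 1.4, alpha 0.2, 80% power. Allocation is 2:1 (104 against 52). Schoenfeld: z = √(127 × 1/3 × 2/3) × ln 1.4 = 5.312 × 0.3365 = 1.787.
- One-sided 0.20: 1.787 − 0.842 = 0.946, power 83%. Adding the interim look at 73 events (power family, ρ = 2) and futility at HR 1.0 gives 80.0% power, an interim bound of HR 1.453 and a final alpha of 0.186. The stated design reproduces.
- Two-sided 0.20, the level in SAP 6.2: 1.787 − 1.282 = 0.506, power 69%.

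The gap between 80% and 69% is a matter of sidedness and a separate point. It explains why the figures below start near 69%.

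**2. Information left when nobody worsens.** Let f be the share at 0–1 on all 11 items at baseline. The documents do not give f, so it is an assumption. With the 20% non-resolution allowance, informative events = 156 × 0.8 × (1 − f). Schoenfeld power at two-sided 0.20:
- f = 0: 124.8 events, 69%
- f = 10%: 112.3 events, 66%
- f = 30%: 87.4 events, 58%

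This is roughly what a test stratified on baseline status can reach when nobody worsens.

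**3. Simulated comparison of tests.** Assumptions: 52 placebo against 104 active; HR 1.4 in patients unresolved at baseline; 80% of placebo resolved by Day 28; two-sided 0.20; records on Days 1–10, 14 and 28, because "Symptoms will be assessed daily for the first 10 days, then at Day 14 and Day 28 and as clinically indicated". Patients who meet the criterion at baseline and never worsen are dated Day 1. Those who worsen follow their arm's time distribution.

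| Share f | Worsening, placebo / active | Unstratified | Protocol severity strata* | Stratified by 11-item baseline status |
|---|---|---|---|---|
| 0% | – | 67–69% | same | same |
| 10% | none | 61–63% | – | 65–66% |
| 30% | none | 47–49% | about 54% | 57–59% |
| 30% | 40% / 29% | 63–64% | – | 67–68% |

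*Assumes that three quarters of baseline-met patients fall in the stratum without moderate or severe symptoms.

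If 40% worsen equally in both arms, stratifying by baseline status gains about 1 point at f = 10% and 2–3 points at f = 30%. Over 0–40% equal worsening, the protocol severity strata gain 1–8 points at f = 30%.

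Restricting to patients unresolved at baseline gives 57–58% at f = 30%. In the 40% / 29% case it gives only 58%, because it discards the benefit of preventing worsening.

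**4. Event counts hide the problem.** At f = 30%, 28–48 of about 139–141 events fall on Day 1, so total events exceed the planned 127 while the informative number is lower.

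**5. False positives (HR 1.0).** At f = 30% with nobody worsening and arms balanced on this group, the unstratified test rejects in about 12% of runs and the test stratified by baseline status in about 20%. Without balance, both reject in 20–21%.

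**6. Robustness.** Simulation error is about 0.5 to 1 point, and model choice moves results by 2–4 points. Setting 80% resolved over all patients (about 73% of placebo) gives 66–67% unstratified at f = 0 and 44–54% at f = 30%. A front-loaded hazard gives 70–71% and 49–58%. Dating these patients to Day 2 instead of Day 1 leaves power unchanged. Age strata were not simulated.

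**The case against.** The strongest reply is that the affected share is unknown and the consequence modest. The severity stratum shows that such patients were allowed, not how many enrolled. SAP 1 gives symptom endpoints less emphasis than viral load when judging proof of concept. Score-0 resolution and total symptom score (SAP 6.4.3.2 to 6.4.3.4) can still register improvement in mild patients. The SAP's ANOVA and logistic models contain treatment only, so the absence of strata may be deliberate. All of this stands, and it limits the weight of the point. It does not remove it: the endpoint is still the declared primary, and the SAP gives no reason for departing from the protocol's test.

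Four stronger readings are tempting but not supported:

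- **A fixed amount of power is lost whatever the test.** This holds only if the drug does not affect worsening. In the 40% / 29% case, stratified power is 67–68%, close to the starting value. Symptom onset within 5 days of first dose makes later worsening plausible.
- **Restoring the strata recovers the full gain.** The larger gains come from stratifying on 11-item baseline status, a factor in neither document. The randomisation strata recover less, because they place a patient whose only moderate symptom is cough, smell or taste with the moderate or severe group.
- **False positives are inflated.** They are not. With arms balanced on this group, the unstratified test is conservative.
- **SAP 4.1 and Appendix 1 give materially conflicting dates.** The last-72-hour wording can be read as a later date. But SAP 4.1 itself sends the reader to Appendix 1, and no records are scheduled between Day 14 and Day 28 to support a very late one. This is mostly wording.

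**Conclusion.** The point holds as a loss of efficiency that the SAP can partly avoid. Patients can meet the primary threshold before dosing, no rule or sensitivity analysis handles them, and the SAP drops the strata that would partly protect the comparison.

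With nobody worsening, the unstratified test gives up about 3–5 points at a 10% share and 9–12 points at a 30% share, compared with stratifying by baseline status. Against the protocol's own severity strata, the difference at 30% is about 5–7 points (54% against 47–49%). These figures rest on an assumed share, HR 1.4 in patients unresolved at baseline, 80% placebo resolution, and three-quarters capture for the protocol strata. The loss is negligible at a share near zero and small if the drug prevents worsening. Part of any loss comes from enrolling patients with little room to improve on this endpoint, and stratifying does not bring that part back.

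This should be fixed. Confidence in the size is medium, because the share is not given.

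**What to change.** Before unblinding:

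1. In SAP 6.4.1, restore the log-rank test stratified by the randomisation factors, severity and age, keeping all ITT patients. If the SAP's silence was meant to keep those strata, one sentence saying so is enough. Optionally, define severity as at least one of the 11 counted symptoms scored 2 or more at baseline. That would be a new factor, not a restoration, and should be labelled as such.
2. Report by arm the number of patients who meet the resolution criterion at baseline. In SAP 6.4.4, add a sensitivity analysis restricted to patients with at least one counted symptom scored 2 or more at baseline, noting that it ignores any benefit from preventing worsening.
3. In SAP 4.1, state that Appendix 1 governs the resolution date. This clarifies wording and does not change power. Appendix 1 accepts a first resolution on a single Day 28 record, so the 72-hour wording should be checked against it at the same time.

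The cost is SAP text and one flag from scores already collected. The drawbacks are possibly small strata when severity is crossed with age, only partial recovery of power, and fewer patients in the restricted analysis.
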